6.3 Agent Accountability

Each institutional Investigator, or a responsible party designated by the Investigator, must maintain a careful record of the inventory and disposition of all drugs received from Basilea, using the NCI Investigational Drug Accountability Record Form.

Upon termination of the study, the Investigator or designee must complete a final inventory of supplies.

7.0 PROCEDURES FOR PATIENT ENTRY ON STUDY

This study is supported by the NCI Cancer Trials Support Unit (CTSU) Regulatory Office and uses the Oncology Patient Enrollment Network (OPEN).

7.1 CTEP Registration Procedures

Food and Drug Administration (FDA) regulations and National Cancer Institute (NCI) and ABTC policy require all investigators participating in any NCI-sponsored clinical trial to register and to renew their registration annually.

Registration requires the submission of:

- a completed *Statement of Investigator Form* (FDA Form 1572) with an original signature
- a current Curriculum Vitae (CV)
- a completed and signed *Supplemental Investigator Data Form* (IDF)
- a completed *Financial Disclosure Form* (FDF) with an original signature

Fillable PDF forms and additional information can be found on the CTEP website at http://ctep.cancer.gov/investigatorResources/investigator_registration.htm.

ABTC # 1601

NCI # ABTC-1601

PI: [name]

For questions about Investigator Registration, please contact the **CTEP Investigator Registration Help Desk** by email [REDACTED].

7.2 Site Registration Requirements – Institutional Review Board Approval

Each Investigator or group of Investigators at a clinical site must obtain Institutional Review Board (IRB) approval for this protocol and submit IRB approval and supporting documentation to the CTSU Regulatory Office before they can enroll patients. Study centers can check the status of their registration packets by querying the Regulatory Support System (RSS) site registration status page of the CTSU member web site by entering credentials at <https://www.ctsu.org> and clicking on the RSS tab.

Site registration documents and a CTSU Transmittal Sheet (on CTSU website) must be submitted to the CTSU Regulatory Office at the following address:

CTSU Regulatory Office
Coalition of National Cancer Cooperative Groups
[REDACTED]
[REDACTED]
[REDACTED]

7.3 Patient Registration

Patient enrollment will be facilitated using OPEN. All site staff will use OPEN. OPEN is a web-based registration system available for ABTC studies from 9 a.m. to 4:30 p.m. Eastern Time. The system can be accessed by entering credentials at <https://www.ctsu.org> and clicking on the OPEN tab, or by entering credentials at the OPEN portal URL <https://open.ctsu.org>.

Since this a Phase I study, patient enrollment for this study will be facilitated using the Slot-Reservation System in conjunction with the registration system on OPEN. Prior to discussing protocol entry with the patient, all site staff must use the CTSU OPEN Slot Reservation System to ensure that a slot on the protocol is available to the patient. Once a slot-reservation confirmation is obtained, site staff may then proceed to enroll patients to this study.

Prior to accessing OPEN, site staff should verify the following:

- All eligibility criteria have been met within the protocol stated timeframes. Site staff should use the registration forms provided on the group web site as a tool to verify eligibility.
- All patients have signed an appropriate consent form and HIPAA authorization form (if applicable).

Access requirements for OPEN:

- Site staff will need to be registered with CTEP and have a valid and active CTEP-IAM account. This is the same account (user id and password) used for credentialing in the CTSU members' web site.

ABTC # 1601

NCI # ABTC-1601

PI: [name]

- To perform registrations, the site user must have been assigned the 'Registrar' role (or equivalent) on the relevant Group or CTSU roster.

The OPEN system will provide the site with a printable confirmation of registration and treatment information. Upon completion of the registration process in OPEN, sites must contact the ABTC Central Office to obtain confirmation of the patient's registration and dose assignment. The local investigational pharmacy should call the ABTC Central Office to confirm the actual dose prior to dispensing the first dose of the first cycle. **No patient may begin treatment until registration AND dose have been confirmed by the ABTC Central Office.**

Further instructional information is provided on the CTSU members' web site [REDACTED]
[REDACTED]

8.0 SAFETY AND QUALITY ASSURANCE

8.1 Safety assessments

Safety assessments will consist of monitoring and recording all AEs and serious AEs, the regular monitoring of hematology, blood chemistry, troponin, pregnancy testing (in women of childbearing potential) and urine values, regular measurement of vital signs, and the performance of physical/neurological examinations, MMSE®s, and ECGs.

8.2 Quality Assurance

8.2.1 Neuropathology

The neuropathologic diagnosis of GBM will be made at the respective institution. If any question arises regarding the accuracy of the neuropathologic diagnosis, slides (and pathological blocks, if necessary) will be reviewed by the central review pathologist. For protocols with "response" as an outcome, all patients with a documented complete response or partial response will have representative pathology slides undergo central review.

8.2.2 Neuroradiology

MRI scans of patients showing tumor response will be centrally reviewed by a neuroradiologist who will independently assess tumor size and compute percent tumor regression.

8.2.3 Neuro-oncology

The local Investigator at the participating institution will communicate to the ABTC Central Office any unexpected neurological effects such as change in seizure frequency, alteration in neuromuscular function, alteration in cognitive function, or fluctuations in serum anticonvulsant drug levels.

8.2.4 Adherence to protocol therapy

As a quality assurance measure for the treatment delivered on this protocol, primary patient records may be reviewed. The records to be examined will be selected retrospectively and at random; complete records must therefore be maintained on each patient treated on the protocol. These records should include primary documentation (e.g., laboratory report slips, X-ray reports, scan reports, pathology reports, physician notes, etc.), which confirm that:

ABTC # 1601

NCI # ABTC-1601

PI: [name]

- The patient met each eligibility criterion.
- Signed informed consent was obtained prior to treatment.
- Treatment was given according to protocol (dated notes about doses given; any reasons for any dose modifications).
- Toxicity was assessed according to protocol (laboratory report slips, etc.).
- Response was assessed according to protocol (MRI scan, lab reports, dated notes on measurements and clinical assessment, as appropriate).
- NCI Drug Accountability Records were maintained for this protocol.

9.0 MONITORING OF PATIENTS

9.1 Table of Required Observations

Table 7 Required observations

	Baseline	Day 1	Weeks 1-6	Weekly	Day 22	Off Treatment (within 7 days)	30 Day Follow-Up
BAL101553			6				
Corticosteroid Dose Evaluation	1					8	
Prior and Concomitant Medications	1,16			3		8	
AE Evaluation	1			3		8	5,12
Brain MRI	1					8	
H&P/Neuro Exam	1				7	8	
KPS	1				7	8	
Mini-Mental State Examination (MMSE®)		20		3, 20			
Vital Signs	1,4			3,4,14		4,8	
CBC, Diff, Platelets	1			2,3		2,8	
Serum Chemistry	1,10			3,10,13,15		8,10	
Cardiac troponin	1			3,15		8	
Echocardiography, cardiac MRI or MUGA	1						
APTT or PTT and INR	1						
Serum Pregnancy Test	9						
ECG	1			17		(8, 17)	
Archived Tumor Tissue	11						
Blood Samples for PK Analyses		18			18		
Study drug dispensing		19		3, 19			

1. All baseline measurements must be done after obtaining written informed consent and must be performed within 14 calendar days prior to first treatment administration except for the baseline MRI, which may be obtained within 21 days prior to first study drug administration, and the corticosteroid dose evaluation, which should be obtained within 5 days prior to the baseline MRI.
2. If ANC < 1500 or platelets < 100,000, CBCs/differentials will be repeated twice a week until counts are recovered (ANC \geq 1500 or platelets \geq 100,000) per protocol. If counts are recovered (ANC \geq 1500 or platelets \geq 100,000) on day of scheduled drawing, do not repeat until next scheduled protocol study visit.
3. ± 1 day
4. Including blood pressure, respiratory rate, heart rate, temperature, weight, height. Weight and height are required at baseline only.

Phase I Study to Determine the Safety and Tolerability of the Oral Microtubule Destabilizer BAL101553 in Combination with Standard Radiation in Patients with *MGMT* Promoter Unmethylated Newly Diagnosed Glioblastoma

ABTC # 1601

NCI # ABTC-1601

PI: [name]

5. Adverse events must be followed for at least 30 days from last dose of BAL101553.
6. BAL101553 is administered orally every day during radiation therapy (see Section [4.4.1](#)). Patients are required to keep a capsule diary (see [Appendix I](#)).
7. ± 3 days
8. Evaluations are to be performed within the 7 days following the off-treatment date, unless indicated. Evaluations that do not need to be repeated include: MRI if performed within the 14 days prior to the off-treatment date; H&P/neuro, KPS, or labs if performed within the 5 days prior to the off-treatment date.
9. For women of child-bearing potential. Pregnancy testing must be performed within 72 hours prior to first study drug administration.
10. Including albumin, alkaline phosphatase, total bilirubin, calcium, creatinine, magnesium, phosphorus, potassium, SGOT, SGPT, sodium.
11. Unstained slides or tumor blocks from initial resection at diagnosis of glioblastoma, dependent on availability (Section [9.5.2](#)).
12. Within +14 days. May be performed at the off-treatment visit if at least 30 days from last dose of BAL101553.
13. A serum sodium level of < 130 mmol/L (CTCAE Grade 3) that is symptomatic or not reversible within 3 days, or that re-occurs upon study drug continuation or re-initiation at the same dose, is a DLT. Under these circumstances, study treatment must be discontinued temporarily or permanently, depending on the improvement/normalization of sodium levels (see Section [5.1](#)). Serum sodium testing must be repeated twice a week until recovered to ≥ 130 mmol/L.
14. If SBP ≥ 160 mmHg or DBP ≥ 100 mmHg, initiate intervention, Section [4.6.2](#). Patients with SBP ≥ 160 mmHg or DBP ≥ 100 mmHg must take BP daily until < 160 mmHg AND DBP < 100 mmHg. Patients should record BP readings in the pill diary ([Appendix I](#))
15. Perform weekly during RT+BAL101553 treatment (Days 8, 15, 22, 29, 36, 43); after RT is complete, perform every other week (Day 57 and off treatment).
16. Record all medications taken within 14 days prior to baseline (screening) visit.
17. ECG assessments to be done pre-dose and 2 h (± 30 mins) post-BAL101553 administration on Days 1, 8, 15, 22, 29 and 36 (± 1 day from Day 8 onwards). A final ECG will be taken within 7 days after the final dose of BAL101553. Patients with any abnormal ECG readings during the study will have an additional ECG performed at the end of the 10-week study period.
18. PK samples will be collected on Days 1 and 22: pre-dose and 0.5 h, 1 h, 2 h (up to 3 h), 4 h, 6 h and 24 h post-dose (see Section [9.5.1](#)).
19. New study drug will be dispensed to patients at study visits at weekly intervals. All safety parameters (including laboratory safety parameters and MMSE[®]) applicable for assessing the ability for a patient to continue receiving study medication must be reviewed at any study visit prior to dispensing new study medication (see Section [5.2](#)).
20. The MMSE^{®,21} will be performed predose on Day 1 (=baseline) and weekly during RT+BAL101553 treatment when no Neuro Exam is planned (Days 8, 15, 29, 36, 43). Based on the MMSE[®] Score, a Neuro Exam will be scheduled within 1 calendar day if both of the following conditions apply: score < 26 and decline against baseline > 3; see Section [5.2.2](#).

IMPORTANT: *The guidance below is subject to applicable local Institutional Policy on telemedicine. In the event that local Institutional Policy regarding telemedicine differs from this guidance, then please follow local Institutional Policy.*

Telemedicine visits may be substituted for in-person clinical trial visits or portions of clinical trial visits where determined to be appropriate, and where determined by the investigator not to increase the participant's risks. Prior to initiating telemedicine for study visits, the study team will explain to the study participant, what a telemedicine visit entails, and confirm that the participant is in agreement and able to proceed with this method. Telemedicine acknowledgement will be obtained in accordance with your institution's guidance for use of telemedicine research. In the event that telemedicine is not deemed to be feasible, the study visit will proceed as an in-person visit. Telemedicine visits will be conducted using HIPAA- compliant methods approved by the Health System and within licensing restrictions.

Informed consent may be obtained in person, or if deemed necessary, via telemedicine.

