5.0 DOSE MODIFICATION FOR TOXICITY

5.1 Dose Limiting Toxicity

A DLT is defined as a clinically-significant AE or abnormal laboratory value assessed as unrelated to disease progression, intercurrent illness, or concomitant medications and meets any of the criteria below. Any DLT must be a toxicity considered at least possibly related to BAL101553 or the combination of BAL101553 and radiation.

Treatment-related DLTs are defined below. Dose limiting toxicities must have an attribution of possible, probable, or definite to BAL101553 or the combination of BAL101553 and radiation. For patients experiencing a DLT, BAL101553 will be interrupted. If the patient recovers (\leq grade 1 [or tolerable grade 2 for non-hematologic toxicity] or \leq baseline), a BAL101553 dose reduction (1 dose level reduction) is required for subsequent doses. Skipped BAL101553 doses will not be made up. If there is any question or clarification required concerning a potential DLT, the treating site should contact the ABTC Central Office to determine patient's DLT status. The ABTC Central Office, with the Study Chair, will make the final decision.

➤ **Hematological toxicities** will be considered dose limiting if any of the following occur and complete blood counts and differentials were obtained according to the mandated schedule (CBC, differential, and platelets drawn twice a week until the ANC \geq 1500/mm³ and platelets \geq 100,000/mm³):

- ANC of $<$ 500/mm³.
- Platelets $<$ 25,000/mm³.
- Febrile neutropenia
- Any hematological toxicity that prevents administration of \geq 80% of the planned BAL101553 dose

Grade 3 or 4 lymphopenia will not be considered a DLT.

➤ **Central nervous system toxicities**

- \geq **Grade 2** central nervous system (CNS) ischemia will be considered a DLT
- \geq **Grade 2** neurological toxicities that interfere with activities of daily living and do not resolve spontaneously or with steroids, anticonvulsants, or electrolyte correction within 2 weeks will be considered a DLT
- Symptomatic CNS hemorrhage of any grade will be considered a DLT.

➤ **Grade 3 and 4 non-hematological, non-CNS toxicities** will be considered dose limiting with the following exceptions:

- Grade 3 nausea, vomiting, or diarrhea without sufficient prophylaxis with a duration $<$ 3 days;
- Alopecia;
- Grade 3 fatigue;
- Grade 3 hyperglycemia that is reversible and without clinical symptoms;

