- Grade 3 electrolyte disturbances that are asymptomatic and reversible within 3 days, and do not re-occur upon continuing or re-initiation at the same dose;
- Grade 3 or 4 hypophosphatemia, unless considered clinically relevant;
- Grade 3 or 4 elevations in alkaline phosphatase;
- Grade 3 hypertension that resolved to \leq Grade 2 hypertension within 1 week either spontaneously or upon implementation of antihypertensive therapy

ABTC # 1601

NCI # ABTC-1601

PI: [name]

- A subject's first episode of deep venous thrombosis (DVT) or pulmonary embolism will not require dose modification.
- **Any adverse event that leads to missing > 6 doses of BAL101553** will be considered dose limiting.
- **Any recording of SBP > 220 mmHg or DBP > 110 mmHg or any Grade 4 hypertension** will be considered dose limiting.

ANY DLT (AS DEFINED ABOVE) CAUSING DELAY IN TREATMENT OF OVER 7 DAYS WITHOUT RECOVERY TO A \leq GRADE 1 OR BASELINE STATUS WOULD RESULT IN TAKING THE PATIENT OFF TREATMENT.

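### Table 7 footnote 2 ends the twice-weekly blood counts when ANC *or* platelets recover, whereas section 5.1 requires both; the footnote should say *and*

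*Protocol*

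**What the plan says.** Three places in the protocol bear on this, and the SAP repeats one of them.

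- **Protocol section 9.1, Table 7, footnote 2.** The trigger is ANC below 1500 or platelets below 100,000. The stop is: "CBCs/differentials will be repeated twice a week until counts are recovered (ANC \geq 1500 or platelets \geq 100,000) per protocol". The next sentence uses the same *or* definition of recovery and tells staff what to do once it is met: "on day of scheduled drawing, do not repeat until next scheduled protocol study visit".
- **Protocol section 5.1.** A haematological toxicity counts as dose limiting if it occurs and "complete blood counts and differentials were obtained according to the mandated schedule". That schedule is spelled out as "CBC, differential, and platelets drawn twice a week until the ANC \geq 1500/mm³ and platelets \geq 100,000/mm³".
- **Protocol section 9.1, Table 7, footnote 14.** The blood pressure rule starts on either limit being exceeded and stops only when both are back in range: patients "must take BP daily until < 160 mmHg AND DBP < 100 mmHg".
- **SAP Table 1, footnote 2.** This carries over the *or* wording from protocol Table 7.

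**The concern.** The footnote and section 5.1 describe the same repeat-count schedule but end it at different points. A site working from the table of required observations can therefore stop drawing while section 5.1 still requires draws.

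What is at stake is the certainty of a DLT call. The exposed patient is one flagged with a low count, followed only weekly under the footnote, and later found with ANC below 500 or platelets below 25,000. Section 5.1's condition on the draw schedule has then not been met, so the DLT is open to question and has to be settled by judgement: the ABTC Central Office, "with the Study Chair, will make the final decision". A patient whose first low count is already at DLT level is not exposed, because no draw has been missed.

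Febrile neutropenia, and haematological toxicity that prevents 80% or more of the planned dose from being given, sit under the same schedule condition, so they do not act as independent safeguards. One criterion does stand outside it: "Any adverse event that leads to missing > 6 doses of BAL101553".

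**Working it through.** The plan gives no figure to reproduce. The check is a comparison of two stopping rules, followed by a count of draws under stated assumptions.

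**Step 1: the rules in each state.** Inputs are footnote 2 (trigger and stop) and section 5.1 (stop).

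| State | Footnote trigger met? | Footnote stop, literal *or* | Footnote stop, pairwise (the count that was low has recovered) | Section 5.1 stop, *and* |
|---|---|---|---|---|
| Both counts adequate | No | Met | Met | Met |
| ANC low only | Yes | Met at once | Not met | Not met |
| Platelets low only | Yes | Met at once | Not met | Not met |
| Both low | Yes | Not met; met when the first count recovers | Not met; unclear when the first count recovers | Not met until both recover |

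Of the three states that trigger extra counts, the literal wording treats two as already recovered; the pairwise reading and section 5.1 treat none that way. In those two states the footnote's trigger and stop hold together, so the rule cancels itself. With *and*, the stop becomes the exact complement of the trigger and agrees with section 5.1 in all four rows.

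**Step 2: size of the gap in draws.** Assumptions:

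- Weekly counts fall on Days 8, 15, 22, 29, 36 and 43. Footnote 15 lists these days for chemistry and troponin; the CBC row names no days.
- The first low count is on Day 8.

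Weekly intervals from Day 8 to Day 43: (43 − 8) / 7 = 5.

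- Section 5.1, a count still low to Day 43: 2 × 5 = 10 later draws.
- Literal footnote, one lineage low to Day 43: weekly only, 5 draws. Lost: 10 − 5 = 5.
- Literal footnote, one lineage low but recovered by the first mid-week draw: only that mid-week draw is missed. Lost: 1.
- Pairwise reading, one lineage low, or both low and recovering together: same as section 5.1. Lost: 0.
- Pairwise reading taken to stop at the first recovery, both low, one recovered by the first mid-week draw and the other low to Day 43: 1 + 5 = 6 draws. Lost: 10 − 6 = 4.

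These are illustrations of the conflict. The documents give no rate of low counts from which to estimate how often any of them would occur.

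**The case against.** The strongest reply is that section 5.1 already states the correct rule and calls its schedule mandated, and that the footnote ends its first sentence by deferring to the protocol. A sensible site would not adopt a reading under which the rule starts and stops at once; it would wait for whichever count was low. On that reading single-lineage cases agree with section 5.1, and the larger draw counts above fall away.

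The route to a lost DLT is also long: a low count, a site that stops early, a later fall to DLT level, and then a decision not to count the event. Nothing in the documents suggests the Central Office and Study Chair would discard it. Detection continues in any case. CBCs remain weekly, and section 4.4.2 requires laboratory review before each weekly dispensing. Section 3.2 requires ANC of at least 1,500 and platelets of at least 100,000 at entry. Section 6.1 lists no neutropenia or thrombocytopenia at oral doses up to 16 mg per day, against a top planned dose of 15 mg. The SAP copy directs no blood draw and feeds no analysis.

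Most of this stands, and it limits the point to a minor one. It does not remove the conflict. The footnote cites no section for the rule it defers to, and its second sentence positively instructs staff not to repeat the count. The pairwise reading still leaves the case of both counts low unresolved. Nor is the rule idle: section 2.2 names blood among the main toxicity targets in the 4-week oral animal studies, and Grade 3 neutropenia was among the DLTs at 90 mg/m² given intravenously. Both are indirect evidence for oral dosing with radiotherapy.

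**Conclusion.** The inconsistency is real and is in the current text. Footnote 2 is wrong as written: its stopping rule contradicts section 5.1 and, read literally, its own trigger. Confidence in the wording mismatch is high; the effect on DLT ascertainment is indirect and rests on the sequence of events described above.

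Per affected patient, under the assumed weekly days and a Day 8 flag, the loss ranges from none to 5 of the draws section 5.1 requires, depending on the reading and on how long the count stays low. The number of such patients cannot be derived from the documents and is probably small. No sample size, escalation rule or planned analysis changes. Severity: minor.

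**What to change.** In protocol Table 7, footnote 2, replace *or* with *and* in both recovery brackets, so that each requires ANC of at least 1500 and platelets of at least 100,000, as section 5.1 does. Keep *or* in the starting trigger. Make the same two replacements in SAP Table 1, footnote 2, for consistency.

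The cost is one word, twice, in each document, and no draw beyond those section 5.1 already mandates. The SAP describes the study as ongoing with 26 patients included; if accrual has ended, a written clarification would serve for any DLT review that remains. The change aligns the two schedules. It leaves in place section 5.1's condition that counts were drawn on schedule.
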